All subjects in the ITT2 Analysis Set who receive at least 1 dose of study drug will be included in the Safety Analysis Set. Subjects will be analyzed according to the actual treatment received.

PK Analysis Set:

All subjects in the ITT2 Analysis Set who have at least 1 measurable plasma or CSF PTC857 concentration will be included in the PK Analysis Set.

The null hypothesis of this study is that the subject ranks based on the composite survival and change from baseline in ALSFRS-R after 24 weeks of treatment are the same in the PTC857 (250 mg BID) and in the placebo versus the alternative that they are different; a 2-sided test at the 5% alpha level will be applied.

The primary efficacy endpoint will be analyzed on the ITT1 Analysis Set at the significance level of 0.05 (2-sided). If p<0.05, then the study will be declared positive.

For the primary efficacy endpoint, subject ranks based on the Combined Assessment of Function and Survival (CAFS) ranking method, will be analyzed when all subjects in the ITT1 Analysis Set finish the Treatment Period (Part A). This analysis will be performed using an analysis of covariance (ANCOVA) model following multiple imputation. Subjects who discontinue from the study prior to Week 24 will have their Week 24 ALSFRS-R score imputed using multiple imputation. The ANCOVA model will include the following covariates: treatment arm (PTC857 and placebo), baseline ALSFRS-R score, the amount of change in the subject's ALSFRS-R score during the Screening Period (<1, 1-2, and 3-4 points total loss), and standard-of-care exposure with rank scores as the response variable. A p value for the difference will be presented.

Safety endpoints (severity and number of TEAEs and TESAEs, change from baseline in clinical laboratory tests, physical examination, vital signs, C-SSRS, and 12-lead ECGs) will be descriptively compared between PTC857 and placebo.

TABLE OF CONTENTS

| TITLE I | PAGE | 1 |
|---------|---|----|
| PROTO | COL IDENTIFIERS AND STUDY PERSONNEL | 3 |
| PTC TH | IERAPEUTICS PROTOCOL APPROVAL SIGNATURES | 5 |
| PRINCI | PAL INVESTIGATOR AGREEMENT AND SIGNATURE | 7 |
| SYNOP | PSIS 8 | |
| TABLE | OF CONTENTS | 19 |
| LIST O | F TABLES | 24 |
| LIST O | F FIGURES | 24 |
| LIST O | F ABBREVIATIONS AND DEFINITIONS OF TERMS | 25 |
| 1. | INTRODUCTION | 28 |
| 1.1. | Background Information. | 28 |
| 1.2. | Name and Description of Investigational Product | 28 |
| 1.3. | Mechanism of Action | 28 |

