|---|--------------------|---------|-----------------------|--------|----------------------|--------------------|------------|--------------------|--------------------|----------------------------------|----------------------------|----------------------|
| | | | | (24 W) | | | | | | | | |
| Study Day | Screening | Day -28 | Day 1 | Day 14 | Day 29 | Day 57 | Day 85 | Day 113 | Day 141 | Day 169 | Day 197 | |
| | (-56 Days) (±5) | (±3) | (- 3) ª | (±3) | (±3) | (±3) | (±3) | (±3) | (±3) | (±3) | (±3) | |
| | | | Baseline ^a | | | | | | | End of Treatment ^b | Follow- Up ^c | ET₫ |
| Telephone call/in-home or in-person visit ^f | IP | PC | IP | PC/IH | PC/IH ^{e,f} | PC/IH ^f | IP | PC/IH ^f | PC/IH ^f | IP | PC | IP |
| COVID-19 PCR | Х | | | | | | | | | | | |
| Informed consent | Х | | | | | | Xg | | | Xh | | |
| Inclusion/exclusion criteria | Х | | | | | | | | | | | |
| Re-evaluation eligibility | | | Х | | | | | | | | | |
| Randomization | | | Х | | | | | | | | | |
| Height | Х | | | | | | | | | | | |
| Weight and BMI | Х | | Х | | | | Х | | | Х | | Х |
| Demographics | Х | | | | | | | | | | | |
| Medical history | Х | | | | | | | | | | | |
| Serum/urine pregnancy test (females only) ⁱ | Х | | Х | | Х | Х | Х | Х | Х | Х | Х | Х |
| FSH measurement ^j | Х | | | | | | | | | | | |
| 12-Lead ECG ^k | Х | | Х | | | | Х | | | Х | | Х |
| Vital signs | X | | Х | | Х | Х | Х | Х | Х | Х | | Х |
| Physical exam ^m | X | | Х | | | | Х | | | Х | | Х |
| Sparse PK blood sampling ⁿ | | | X | | | | Х | | | X | | X |

| | | | Treatment Period (24 W) | | | | | | | EOS/ FU | Early Termination | |
|--|--------------------|---------|-------------------------|--------|--------|--------|--------|---------|---------|----------------------------------|----------------------|-----|
| Study Day | Screening | Day -28 | Day 1 | Day 14 | Day 29 | Day 57 | Day 85 | Day 113 | Day 141 | Day 169 | Day 197 | |
| | (-56 Days) (±5) | (±3) | (-3)ª | (±3) | (±3) | (±3) | (±3) | (±3) | (±3) | (±3) | (±3) | |
| | | | Baseline ^a | | | | | | | End of Treatment ^b | Follow- Up° | ET₫ |
| Clinical laboratory tests ^o | Х | | Х | Xp | Х | Х | Х | | | Х | | Х |
| CSF for biomarkers ^{q,r} | | | Х | | | | | | | Х | | Х |
| Laboratory biomarkers (blood and urine)s | | | Х | | | | Х | | | Х | | Х |
| ALSFRS-R ^t | Х | Х | Х | | Х | Х | Х | Х | Х | Х | Х | Х |
| PFTs ^u | Х | | Х | | | | Х | | | Х | | Х |
| ALS CBS | Х | | Х | | | | Х | | | Х | | Х |

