7.1.7. Plasma-, Urine-, and CSF-Based Biomarkers

Plasma- and CSF-based biomarker levels will be performed to evaluate PTC857's biochemical activity and ability to modulate key aspects of disease pathology.

Plasma-based biomarkers will be collected in all subjects. CSF-based biomarkers will only be collected at a subset of clinical sites, as follows:

- Plasma: (target engagement) hydroxyeicosatetraenoic acid panel, (disease-specific biomarkers) NfL and ferritin, and (oxidative stress) 4-hydroxynonenal (4HNE)
- Urine: p75 neurotrophin receptor (p75NTR) fragment extracellular domain normalized to creatinine
- CSF: (disease-specific biomarker) NfL

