8.1. Statistical Hypotheses

For the primary efficacy endpoint, the null hypothesis of this study is that the subject ranks based on the composite survival and change from baseline in ALSFRS-R after the 24-week Treatment Period are the same in the PTC857 group and in the placebo group versus the alternative that they are different.

The primary efficacy endpoint will be analyzed on the ITT1 Analysis Set at the significance level of 0.05 (2-sided). If p<0.05, then the study will be declared positive.

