1.5. Sample Size

For the primary efficacy endpoint, the combined assessment of ALSFRS-R and survival after 24 weeks of treatment, 307 subjects in the ITT1 Analysis Set (205 in the PTC857 group and 102 in the placebo group, based on a 2:1 randomization ratio) will provide approximately 85% power to detect a treatment difference of 2 points with a standard deviation of 5.3, based on a 2-sided 0.05 level Joint Rank Test, and assuming 24-week survival rates of 96.5% and 95% in the PTC857 and placebo groups, respectively. These assumptions took into consideration data from 2 clinical

studies in ALS which reached statistical significance for their primary endpoints that reported overall death rates of 0% and 5% (Edaravone (MCl-186) ALS 19 Study Writing Group 2017 and Paganoni, 2020) A standard deviation of 5.3 points for the ALSFRS-R score at Week 24, among treated subjects was reported for the edaravone study (Edaravone (MCl-186) ALS 19 Study Writing Group 2017).

Assuming approximately 10% of randomized subjects will not meet the ITT1 Analysis Set definition, then approximately 340 subjects will be randomized to ensure that 307 subjects are randomized into the ITT1 Analysis Set. Given that the primary analysis incorporates deaths as a combined endpoint, and a fully imputed analysis dataset is utilized in the analysis, additional enrollment and randomization to make up for discontinued subjects is not planned. This document clarifies a typographical error in the study protocol that incorrectly indicated a treatment difference of 2.5 points instead of 2 points, is of interest.

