5. EFFICACY ANALYSIS

5.1. Analysis of the Primary Efficacy Endpoint

The primary efficacy variable, subject ranks based on the combined assessment of function and survival (CAFS) after 24 weeks of treatment will be performed using an analysis of covariance model (ANCOVA) following multiple imputation. The estimand framework described in Section 3.3.1 will be used. The ANCOVA model will contain the following main effects: treatment (PTC857 or placebo), the amount of change in the subject's ALSFRS-R score during the Screening Period (<1, 1-2, or 3-4-points total loss), TRICALS risk profile (continuous), use of Approved Background Therapy for ALS (Yes [either riluzole, edaravone, or sodium phenylbutyrate/taurursodiol], No). Baseline ALSFRS-R score (continuous) and The TRICALS risk profile (continuous) will be included as covariates.

Subjects who discontinue from the study prior to week 24 will have their week 24 ALSFRS-R score imputed using the same datasets described in Section 5.5.1.2. In each of the 100 imputed datasets, subjects who die will have their death day (study day) incorporated as part of the combined assessment of function and survival.

The p-value for the treatment comparison (PTC857 versus Placebo) at week 24, estimate of LSMEANS for the treatment differences (PTC857 – Placebo), and the two-sided 95% confidence interval of the LSMEANS difference will be presented for the ITT1 analysis set (obtained from PROC MIANALYZE in SAS). If the p-value for the treatment arm comparisons at week 24 is less than 0.05, then the study will be declared as positive.

This analysis will also be repeated for the ITT2 analysis set and a nominal p-value for treatment arm comparison at week 24 presented.

In addition, averaged win probability (Rubin's rule) and a win-odds, will also be presented.

$$\label{eq:winprobability} Win\ probability(\theta) = 0.5 + \frac{\bar{R}_i - \bar{R}_j}{N_i + N_j} & Where: \\ \bar{R}_i = \ mean\ ranks\ for\ treatment\ groups_{i,j} \\ N_i = \ No.\ subjects\ in\ treatment\ groups_{i,j} \\ \end{cases}$$

$$Win\ odds = \frac{\theta}{(1-\theta)}$$

Given the difficulties in interpreting and quantifying the treatment effect from the CAFS analysis, results from the MMRM analysis in ALSFRS at week 24 (Section 5.5) will be used to describe the treatment effect in terms of loss of function). Similarly, survival differences will be described using results from the Survival analysis (Section 5.7)

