5.6. Subgroup Analyses for Efficacy

To explore the uniformity of the overall treatment effect in subgroups, change from baseline in ALSFRS-R at Week 24 for the subgroups listed below. This analysis will be performed using the MMRM analysis described in Section 5.2, with a treatment by subgroup interaction term added to the model. Subgroups with too few subjects resulting in model non-convergence will be summarized using descriptive summaries of the change from baseline in ALSFRS-R score at week 24.

- Sex (male, female)
- Race (white, non-white)
- Geographic region (North America, Europe, South America, Asia)
- Age at baseline ($<65, \ge 65$ years)
- Slow vital capacity at baseline (<80%, $\ge 80\%$)
- Definite and probable ALS at screening
- Duration of symptoms (<12 months, ≥ 12 months)
- TRICALS Risk Profile (< -4, \ge -4)
- Kings' Stage (1, 2, 3)
- Plasma NfL at baseline (< median value, ≥ median value)
- Decline in ALSFRS-R score during the 8-week screening period (1-2, 2-4, 1-4)
- Use of approved background therapy for ALS (Yes, No)
- Decline in ALSFRS-R score during the 8-week screening period (<4 vs >4) [*]
- Site of ALS onset (limbs, bulbar, other)
- Baseline ALSFRS-R (<41, >=41)
- Family history of ALS (yes, no)

[*] ITT2 analysis set

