14. APPENDIX 4: SAS CODE

Mixed Model Repeated Measure

The following is example SAS syntax for producing least squares estimates, for the MMRM analysis:

```
proc mixed data=ALSFRS_LONG method=reml;
  class ID TRTRND(ref="0") STADCARE(ref="3") CHANGE(ref="<1")
TIME(ref="baseline");
  model DELFRS = TIME VALUEBL CHANGE STADCARE TIME*TRTRND TIME*VALUEBL TRP
  TIME*TRP / ddfm=kr solution;
  repeated TIME / type=UN subject=id;
  lsmeans trtrnd*TIME /cl pdiff=control('0' '5')cl;
  run;</pre>
```

where id is the subject identifier, trtrnd is the randomized treatment arm, stadcare is a factor variable for the SoC stratification group at baseline, change is the amount of change in the subject's ALSFRS-R score during the Screening Period, time is the categorical variable for study visit, Valuebl is the baseline ALSFRS-R score, TRP represents the TRICALS risk profile at baseline, and the response variable DELFRS is the change from baseline in ALSFRS-R score.:

ANCOVA with Multiple Imputation

SAS code for the ALSFRS-R endpoint at 24 weeks:

```
proc mi data = ALSFRS_DATA out = ALSFRS_DATA_OUT
    seed = 20221219 nimpute = 100 noprint;
    class trtrnd stadcare change sex;
    var trtrnd Valuebl change stadcare sex age trp
    ALSFRS_R_4 ALSFRS_R_8 ALSFRS_R_12 ALSFRS_R_16 ALSFRS_R_20 ALSFRS_R_24;
    fcs reg(ALSFRS_R_4 ALSFRS_R_8 ALSFRS_R_12 ALSFRS_R_16 ALSFRS_R_20
    ALSFRS_R_24);
    run;
```

The next set of code performs the analyses for the ALSFRS-R 24-week endpoint:

```
proc reg data=ALSFRS_DATA_OUT utset=outreg covout noprint;
  model ALSFRS_24 = trtrnd Valuebl change stadcare TRP;
  by _Imputation_;
  run;
```

This step will combine the results:

```
proc mianalyze data=outreg;
  modeleffects Intercept trtrnd Valuebl change stadcare TRP;
  run;
```

Pattern Mixture Model

The strategy implemented to carry out the control-based PMM assumes that all other variables, except ALSFRS-R, with missing data are first imputed using the FCS approached outlined in the previous sensitivity analysis, with 100 imputation datasets. These data are stored in DATAIN_IMP0, which contains a variable _Imputation_ to distinguish between multiple copies of the original input data. In the next step missing ALSFRS-R at the first time point will be imputed (the first time-point that has some missing data). To use the control-based imputation

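### Baseline plasma NfL is planned for every subject, yet the primary rank ANCOVA, the ALSFRS-R models and the imputation model do not use it: a possible missed gain in precision, not an error

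*Protocol*

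**What the plan says.** The protocol model (Synopsis, Statistical Methods, and Section 8.4.1) starts with "The ANCOVA model will include the following covariates: treatment arm (PTC857 and placebo), baseline ALSFRS-R score" and goes on to screening-period ALSFRS-R change and standard-of-care exposure. It is not the operative text: SAP Section 1 says that differences in the SAP override the protocol.

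SAP Section 5.1 has treatment, screening-period ALSFRS-R change and background ALS therapy (yes/no), and then states: "Baseline ALSFRS-R score (continuous) and The TRICALS risk profile (continuous) will be included as covariates". The October 2024 erratum confirms that TRICALS enters once, as a covariate. The ALSFRS-R MMRM (SAP 5.5.1.1) and the ANCOVA after imputation (5.5.1.2) use the same baseline variables. The primary analysis takes its imputed Week 24 scores from the 5.5.1.2 datasets. In Appendix 4 the PROC MI statement for these reads "var trtrnd Valuebl change stadcare sex age trp", followed by ALSFRS-R at Weeks 4 to 24. NfL appears in none of them.

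On availability, Protocol Section 7.1.7 says "Plasma-based biomarkers will be collected in all subjects" and lists NfL among the disease-specific plasma markers. The Table 1 row for blood and urine laboratory biomarkers is marked at Day 1. Change in log plasma NfL is step 5 of the fixed sequence (SAP 4.6). SAP 5.5.2 already fixes the log transform, sets values below quantification to half the LLOQ, and uses baseline log NfL as a covariate in the NfL model. SAP 5.6 has an ALSFRS-R subgroup defined by "Plasma NfL at baseline (< median value, ≥ median value").

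**The concern.** Adjusting for a value measured before treatment that predicts the outcome shrinks the residual variance without biasing the treatment comparison. Here the sample is already scheduled, the assay is already needed for Part A, and the transformation is already written down. The documents give no reason for leaving the variable out.

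The SAP itself accepts this kind of adjustment. It added TRICALS to the primary model beyond the protocol's list, and it carries sex and age in the imputation model though they are not in the ANCOVA.

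Two features raise the stakes a little. Testing is fixed-sequence, and the primary test and the next three (ALSFRS-R change in ITT1 and ITT2, CAFS in ITT2) all use models without NfL, so precision at the first gate matters for every later claim. Also, SAP 1.5 plans no extra enrolment for discontinuation and relies on imputation, which SAP 4.7 bases on missing at random. A predictor of decline in the imputation model would make that assumption easier to accept.

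**Working it through.** **Inputs from the documents.** Two-sided alpha 0.05 (Protocol 8.1). ITT1 of 307, split 205:102, with 24-week survival of 96.5% and 95% (SAP 1.5). SAP 1.5 says this size "will provide approximately 85% power to detect a treatment difference of 2 points with a standard deviation of 5.3"; it calls the protocol's 2.5 points a typographical error.

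**Inputs assumed.** The partial R-squared (R²) of baseline log NfL with the Week 24 outcome, given the covariates already in the model, is not in the documents; range 0 to 0.15. The share of survivor variance explained by the existing covariates is not given either; 10% and 25% are used.

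**Step 1: reproduce the plan's figure.** The joint rank test was simulated 20,000 times with deaths ranked below all survivors by death time, survivors normal with SD 5.3, and no covariates. Power is 85.0% at 2 points, which matches the SAP, and 95.9% at 2.5 points. The 85% therefore depends on neither NfL nor any other covariate.

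**Step 2: gain from an 85% start.** The noncentrality is 1.960 + 1.036 = 2.996. With NfL added, power = Φ(2.996/√(1 − R²) − 1.960), equivalent N = 307/(1 − R²), and the standard error falls by 1 − √(1 − R²).

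| Assumed R² | Power | Equivalent N | SE reduction |
|---|---|---|---|
| 0 | 85.0% | 307 | 0% |
| 0.02 | 85.7% | 313 | 1.0% |
| 0.05 | 86.7% | 323 | 2.5% |
| 0.10 | 88.5% | 341 | 5.1% |
| 0.15 | 90.1% | 361 | 7.8% |

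For example, at 0.10: 2.996/0.9487 = 3.158; 3.158 − 1.960 = 1.198; Φ(1.198) = 88.5%.

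**Step 3: gain once the existing covariates count.** Step 2 starts from an unadjusted 85%, but the planned model is already adjusted. A rank ANCOVA was simulated (2 points, 4,000 trials per row, models with and without NfL fitted to the same trials). R² here is among survivors, and deaths are independent of the covariates. Gains are from unrounded figures.

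| Existing covariates explain | R² of NfL | Power without | Power with | Gain (points) |
|---|---|---|---|---|
| 10% | 0 | 87.7% | 87.6% | about 0 |
| 10% | 0.02 | 86.5% | 87.1% | 0.6 |
| 10% | 0.05 | 87.7% | 89.2% | 1.5 |
| 10% | 0.10 | 87.1% | 89.5% | 2.5 |
| 10% | 0.15 | 87.4% | 91.2% | 3.8 |
| 25% | 0 | 91.2% | 91.2% | about 0 |
| 25% | 0.02 | 90.8% | 91.1% | 0.3 |
| 25% | 0.05 | 91.8% | 92.7% | 0.9 |
| 25% | 0.10 | 91.4% | 93.3% | 2.0 |
| 25% | 0.15 | 92.0% | 94.7% | 2.6 |

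A single power near 88% has simulation error √(0.88 × 0.12/4000) = 0.5 point, so small movements between rows are noise. At R² = 0 the covariate costs one degree of freedom and has no visible effect on power. The effect of NfL on the imputation itself was not quantified.

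**The case against.** The strongest reply is that the key premise is missing from the documents. Protocol 7.1.7 collects NfL to show biochemical activity and modulation of disease, which is a pharmacodynamic purpose. The median-split subgroup explores whether the effect is uniform; it does not establish prognosis. A reader might infer that precision is definitely being given up. The documents do not support that, because the range of possible gain includes zero.

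A reader might also infer that, since none of the seven TRICALS inputs is NfL, its information must be absent from the model. That does not follow. Correlated covariates can carry it: TRICALS includes vital capacity and ALSFRS-R progression rate, and the model also holds baseline ALSFRS-R and screening-period decline. Only what NfL adds beyond these counts.

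Nor do the documents say that NfL is measured predose in every subject. Collection is planned in all. The biomarker blood is tied to the timing of the clinical laboratory tests, and predose is inferred from fasted laboratory sampling, dosing with meals and the SAP baseline definition.

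The imputation argument is modest. PROC MI already uses the available ALSFRS-R scores at Weeks 4 to 20, early terminators who consent are followed about every 28 days, and deaths are ranked by death day rather than by an imputed score.

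Finally, SAP Section 5 was rewritten after FDA feedback and the SAP is final at version 2.0, so changing the primary model needs a formal amendment.

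All of this stands and limits the claim to a possible gain. None of it shows a bias or a material cost from adding the covariate.

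**Conclusion.** The omission is confirmed in the operative SAP models and is best read as a missed option for efficiency. It is not a bias, an alpha problem or a shortfall in the stated power. The gain rests wholly on the assumed R² of 0 to 0.15: 0 to about 5 points from 85%, or about 0 to 4 points from the 87% to 92% that the existing covariates may already provide if they explain 10% to 25% of survivor variance. Because the downside is about one degree of freedom and the data are already planned, the change is worth making even though its benefit cannot be established from the documents.

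**What to change.** Before Part A unblinding, amend the SAP as follows.

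- Add baseline log plasma NfL, continuous, with values below quantification set to half the LLOQ as in SAP 5.5.2, as a covariate in Sections 5.1, 5.5.1.1 and 5.5.1.2 for ITT1 and ITT2. For the MMRM, state whether it also enters by visit, as the other continuous covariates do.
- Add the same variable to the PROC MI variable list in Appendix 4.
- Specify a treatment-blind rule for a missing baseline value, for example the overall median, applied before imputation so that both models use the same value and no subject is dropped.

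If unblinding has passed, leave the primary model alone and report the NfL-adjusted result only as a labelled supplementary analysis. If the sponsor prefers not to adjust, a sentence recording the reason would close the point.

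The cost is a short SAP amendment, one extra variable in the programs, one missing-value rule and about one degree of freedom in the ANCOVA. No new sample or assay is needed.

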| 16.1. | Prohibited Medications During the Course of the Study | 105 |
| | LIST OF TABLES | |
| Table 1: | Schedule of Assessments for Screening and Treatment Periods (Part A) | 39 |
| Table 2: | Schedule of Assessments for the Long-Term Extension Period (Part B) | 45 |
| Table 3: | Schedule of Assessments for the Continued Long-Term Extension Period (Part C) | 47 |
| Table 4: | Investigational Product | 57 |
| Table 5: | Summary of Clinical Laboratory Tests | 68 |
| Table 6: | Investigator Site Requirements for Recording/Reporting Adverse Events | 72 |
| Table 7: | Grading of Adverse Events | 74 |
| Table 8: | Relationship of Study Intervention to Adverse Event | 75 |
| Table 9: | Investigator Site Requirements for Recording/Reporting Medication Errors | 80 |
| Table 10: | Strong/Moderate Inhibitors of CYP Enzymes | 106 |
| Table 11: | Strong/Moderate Inducers of CYP Enzymes | 106 |
| | LIST OF FIGURES | |
| Figure 1: | Proposed Mechanism of Action of PTC857 | 29 |
| Figure 2: | Study Design | 37 |

LIST OF ABBREVIATIONS AND DEFINITIONS OF TERMS

| Abbreviation or | Explanation |
|----------------------|---|
| Specialized Term | |
| β-HCG | Beta human chorionic gonadotropin |
| λz | Apparent terminal rate constant |
| 12-HETE | 12-Hydroxyeicosatetraenoic acid |
| 15-HETE | 15-Hydroxyeicosatetraenoic acid |
| 15-LO | 15-Lipoxygenase |
| 4HNE | 4-Hydroxynonenal |
| AE | Adverse event |
| AESI | Adverse event of special interest |
| ALS | Amyotrophic lateral sclerosis |
| ALS CBS | Amyotrophic lateral sclerosis Cognitive Behavioral Screen |
| ALSAQ-40 | 40-item Amyotrophic Lateral Sclerosis Assessment Questionnaire |
| ALSFRS-R | ALS Functional Rating Scale-Revised |
| ALT | Alanine aminotransferase |
| ANCOVA | Analysis of covariance |
| aPTT | Activated partial thromboplastin time |
| AST | Aspartate aminotransferase |
| AUC | Area under the concentration-time curve |
| AUC _{0-inf} | AUC from time zero to infinity |
| AUC _{0-t} | AUC from time zero to time of last non-zero (measurable or sampled) |
| | concentration |
| BMI | Body mass index |
| CAFS | Combined Assessment of Function and Survival |
| Cavg | Average concentration over a dosing interval |
| CL/F | Total body clearance |
| C _{max} | Maximum observed concentration |
| CNG | Cynomolgus |
| COVID-19 | Coronavirus disease 2019 |
| CRO | Contract research organization |
| CSF | Cerebrospinal fluid |
| C-SSRS | Columbia-Suicide Severity Rating Scale |
| CTCAE | Common Terminology Criteria for Adverse Events |
| CTIS | Clinical Trials Information System |
| Ctrough | Plasma concentration on Day 29 prior to the morning dose |
| CV | Cardiovascular |
| CYP | Cytochrome P450 |
| DDI | Drug-drug interaction |
| DSMB | Data and Safety Monitoring Board |
| ECG | Electrocardiogram |
| EDC | Electronic data capture |
| eCRF | Electronic data capture Electronic case report form |
| eGFR | Estimated glomerular filtration rate |
| EOS | End of study |
| EQ-5D-5L | Five-level European quality of life five-dimensional questionnaire |
| FSH | Follicle-stimulating hormone |
| FU | Follow-up |
| GCP | Good Clinical Practice |
| | |
| GGT | Gamma-glutamyltransferase |
| GPX4 | Glutathione peroxidase 4 |
| HDL | High-density lipoprotein |

| Abbreviation or | Explanation |
|----------------------|---|
| Specialized Term | |
| HETE | Hydroxyeicosatetraenoic acid |
| IB | Investigator's Brochure |
| ICF | Informed Consent Form |
| IEC | Independent ethics committee |
| IH | In-home |
| INR | International normalized ratio |
| IP | In-person |
| IRB | Institutional Review Board |
| ITT1 | Intent-to-Treat 1 |
| ITT2 | Intent-to-Treat 2 |
| IUPAC | International Union of Pure and Applied Chemistry |
| K ₂ -EDTA | Dipotassium ethylenediaminetetraacetic acid |
| LC-MS/MS | Liquid chromatography with tandem mass spectrometry |
| LDH | Lactate dehydrogenase |
| LDL | Low-density lipoprotein |
| LFT | Liver function test |
| LTE | Long-Term Extension |
| MedDRA | Medical Dictionary for Regulatory Activities |
| NfL | Neurofilament light chain |
| NOAEL | No-observed-adverse-effect level |
| NOEL | No-observed-effect level |
| OTC | Over-the-counter |
| p75NTR | p75 neurotrophin receptor |
| PC | Telephone call |
| PCR | Polymerase chain reaction |
| PD | Pharmacodynamic(s) |
| PFT | Pulmonary function test |
| PI | Principal investigator |
| PK | Pharmacokinetic(s) |
| PP | Per Protocol |
| PT | Prothrombin time |
| RBC | Red blood cell |
| ROS | Reactive oxygen species |
| RSI | Reference Safety Information |
| SAE | Serious adverse event |
| RSL3 | RAS-selective lethal |
| SAP | Statistical Analysis Plan |
| SARS-CoV-2 | Severe acute respiratory syndrome coronavirus 2 |
| SNIP | Sniff Nasal Inspiratory Pressure |
| SOC | System Organ Class |
| SpO ₂ | Oxygen saturation |
| SUSAR | Suspected unexpected serious adverse reaction |
| T _{1/2} | Apparent terminal half-life |
| TEAE | Treatment-emergent adverse event |
| TESAE | Treatment-emergent serious adverse event |
| T _{max} | Time to reach C _{max} |
| ULN | Upper limit of normal |
| UN | Unstructured covariance matrix |
| USM | Urgent safety measure |
| WBC | White blood cell |
| WHO | World Health Organization |
| | Trong trough organization |

| Abbreviation or Specialized Term | Explanation |
|-------------------------------------|---------------------------------|
| WOCBP | Woman of childbearing potential |

